probe data from the SCEDs will be provided in the supplemental materials for the 10 participants whose data have not been reported previously.

Accuracy of articulation of two sets of experimental words (see "Experimental Stimuli") was measured repeatedly prior to treatment (see "Probes" for additional detail). For each participant, treatment (SPT-Random [SPT-R] or SPT-Blocked [SPT-B]) was then applied to one set of experimental words while probing continued with both experimental sets. A two week, notreatment interval followed the first treatment phase and a short-term maintenance probe was completed at the end of the interval. Repeated probing of the set of items to be treated in the second treatment phase during the no treatment interval (as part of the SCED) ensured that performance was stable prior to the application of treatment with that set. Then, the alternate treatment was applied to the remaining set of items. Follow-up probes were conducted at 2, 6, and 10 weeks following the second treatment phase. Please see Wambaugh et al. (2014, 2016) for description of the SCED component.

Treatment Order and Experimental Set Assignment. Quasi-randomized assignment was combined with participant matching to assign participants to one of two treatment orderings (i.e., SPT-R → SPT-B or SPT-B → SPT-R). We aimed to have a balance of aphasia type, aphasia severity and AOS severity reflected in the treatment orders. The first participant enrolled was randomly assigned to a treatment condition. Each subsequently enrolled participant was "matched" to a previously enrolled participant and assigned to the opposite group if he/she had the same aphasia type, had an AQ within 10 points of the match, and had the same AOS severity rating. When a match did not exist, then the participant was randomly assigned to a treatment order. Treatment order assignment is shown in Table 2. Participant matching for treatment order is shown in Supplemental Appendix B: aphasia severity was within 10 AQ points for 8/10

matches, aphasia type was the same for 9/10 matches, and AOS severity was the same for 8/10 matches. Please note that the purpose of the investigation was not to compare performance across groups as all participants received both treatments. The matching and random assignment was conducted to minimize possible confounds associated with treatment order.

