## **Statistical Analyses**

## **Effect Sizes**

Six separate sets of effect size values were calculated for each participant as an indication of magnitude of change for *treated items*: 1) pre-treatment/baseline vs. end of SPT-R treatment phase – Random Phase Items – both subsets; 2) pre-treatment vs. 2-week follow-up – Random Phase Items – both subsets; 3) pre-treatment vs. 10-week follow-up – Random Phase Items – both subsets, 4) pre-treatment vs. end of SPT-B treatment phase – Blocked Phase Items – both subsets; and 5) pre-treatment vs. 2-week follow-up – Blocked Phase Items – both subsets; and 6) pre-treatment vs. 10-week follow-up – Blocked Phase Items – both subsets. This resulted in twelve Δ-values for treated items per individual. Six additional sets of effect size values were also calculated for untreated (generalization) items with comparisons being analogous to those of treatment items.

For the pre-treatment versus end of treatment comparisons, the five baseline probes immediately preceding application of treatment were used along with the final two probes completed during the treatment phase. For the pre-treatment versus two-week follow-up comparisons, the five baseline probes immediately preceding treatment were used with the 2-week follow-up probe that followed completion of that phase of treatment. For the 10-week comparisons, the five baseline probes immediately preceding the treatment phase were also used with the probe that occurred 10 weeks following the treatment phase. Because the experimental design was a cross-over design with only a two-week no-treatment interval, the 10-week follow up probes for the first treated sets fell at approximately two weeks after the conclusion of all treatment (i.e., there was not a 10-week no treatment interval and 10 weeks after the first treatment phase occurred about 2 weeks after the second treatment phase). For the second treated sets, the 10-week follow up

probes were those conducted at 10 weeks following all treatment. For the two participants with shortened treatment phases, the 10 week follow-up point for the first phase of treatment fell at approximately 6 weeks post all treatment.

The  $\Delta$ -values were derived using the following equation:  $ES = (M_{A2} - M_{A1}) / SD_{A1}$ . In this equation, "A1" indicates the baseline values and "A2" indicates the comparison values (i.e., end of treatment, 2 week follow up, or 10 week follow up).

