Bailey et al. (2015) benchmarks: small = 2.25, medium = 3.75, large = 6.66 for baseline to treatment phase comparisons and small = 2.59, medium, = 4.23, large = 6.47 for baseline to follow-up phase comparisons

Paired t-tests with were utilized to compare the effect sizes obtained for SPT-R versus SPT-B. Normality tests were passed and one-tailed p values were obtained. There was not a significant difference in the sample means for *treated item* effect sizes associated with the end of treatment (p = .08), 2-week follow-up phases (p=.105), or 10-week follow up phases (p=.254) for SPT-R treated items versus the SPT-B treated items.

For the *untreated* (generalization items), there were also no significant differences in the sample means for the three measurement conditions: end of treatment – p = .186; 2-week follow-up – p = .236; and 10-week follow-up – p = .212.

For all paired t-tests describe above, power was below the desired power of .80 and negative findings should be interpreted cautiously.

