Comparisons of average group percent change were completed using parametric statistics (i.e., dependent t-tests, one-tailed) when possible and the nonparametric analogs when normality tests were failed (i.e., Wilcoxon Signed Rank tests). The Wilcoxon Signed Rank test indicated that the percent change in SPT-R treated items (65.5%) was statistically significantly greater than the change in SPT-B treated items (51%) for the last probe of the treatment phase: p = .022. Similarly, the sample mean percent change for SPT-R treatment items at 2-week follow-up (58.5%) was statistically significantly greater than the sample mean percent change for SPT-B treatment items at 2-weeks follow-up (45.8%): p = .016. For the 10-week follow-up comparison, a paired t-test was employed; the sample mean percent change of the SPT-R treated items (46.25%) exceeded the mean percent change of SPT-B items (38%) by an amount that is greater than would be expected by chance: p = .043. For the generalization items, no statistically significant differences were found for any of the measurement times: last treatment probe (p = .488), the 2-week follow-up probe (p = .477) and the 10-week follow-up probe (p = .396). As with the effect size data comparisons, the comparisons involving the percent change data were underpowered.

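### The two-order crossover is compared by paired tests with no period term and no results by order, although the 10-week probe is timed differently in the two periods

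*SAP*

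**What the plan says.** The protocol (Experimental Design; Treatment Order and Experimental Set Assignment) describes a two-phase crossover with two orders, SPT-R then SPT-B or the reverse. A participant who matched an earlier one on aphasia type, AQ and AOS severity was given the opposite order. Otherwise: "When a match did not exist, then the participant was randomly assigned to a treatment order". Ten matches are reported, not all of them complete: "aphasia severity was within 10 AQ points for 8/10", with aphasia type equal in 9/10 and AOS severity in 8/10. For the order of each participant the protocol points to a table that is not in the text available for this review.

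The SAP analyses the contrast within participants. Under Effect Sizes: "Paired t-tests with were utilized to compare the effect sizes obtained for SPT-R versus SPT-B". Under Percent Change Over Highest Baseline Performance: "Comparisons of average group percent change were completed using parametric statistics (i.e., dependent t-tests, one-tailed) when possible", with signed-rank tests where normality failed, and "For the 10-week follow-up comparison, a paired t-test was employed". No period or order term is named, and Tables 1 to 4 are not split by order.

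On timing, Effect Sizes says that "the 10-week follow up probes for the first treated sets fell at approximately two weeks after the conclusion of all treatment". For second-treated sets, the "probes were those conducted at 10 weeks following all treatment". For the two participants with shortened phases, "the 10 week follow-up point for the first phase of treatment fell at approximately 6 weeks post all treatment".

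**The concern.** A paired test on the SPT-R minus SPT-B difference ignores which treatment came first. If first-treated and second-treated sets differ systematically, that difference adds noise to the paired test and, when the two orders have unequal numbers, shifts the mean.

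At 10 weeks there is a concrete reason to expect such a difference. The first-treated set is probed shortly after a whole further treatment phase on other words. The second-treated set is probed after 10 weeks without treatment. The end-of-treatment and 2-week probes do not have this asymmetry. Among the three percent-change results that the SAP reports as significant (p = .022, .016 and .043), the 10-week one is both the nearest to .05 and the one with the timing difference.

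**Working it through.** **Inputs.** N = 20. 10-week percent change, treated items: means 46.25 and 38, SDs 32.1 and 26.3, one-tailed paired t p = .043 (SAP Table 3 and the text after Table 4). End-of-treatment effect size: 9.203 and 7.389, p = .08 (SAP Table 1 and Effect Sizes). The documents give no period difference, so every value of P below is assumed. They state no alpha, so .05 is assumed. I take the 10-week percent-change score to use the same probe as the 10-week effect size.

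**Stated figure.** The SD of the paired differences is not given, so .043 cannot be recomputed forward, only checked for feasibility. Difference 8.25; t(19 df) at one-tailed .043 = 1.811; SE = 8.25/1.811 = 4.556; SD = 4.556 × √20 = 20.37. The implied within-person correlation is (32.1² + 26.3² − 20.37²)/(2 × 32.1 × 26.3) = .77, which is possible. The unadjusted two-sided 95% CI is 8.25 ± 2.093 × 4.556 = −1.3 to 17.8 points.

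**Period-adjusted version.** Let n1 be the number with SPT-R first, n2 the number with SPT-B first, and P the first-minus-second-set difference.

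- Bias of the unadjusted mean = P(n1 − n2)/20; adjusted effect = 8.25 − bias.
- Within-order variance V = (19 × SD² − 4 n1 n2 P²/20)/18.
- SE = 0.5 × √[V(1/n1 + 1/n2)], 18 df.

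Example, 12:8 and P = 5: bias = 5 × 4/20 = 1.0, effect 7.25; V = (19 × 20.37² − 480)/18 = 411.5; SE = 0.5 × √(411.5 × 0.2083) = 4.629; t = 1.566; p = .067.

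| Split | P | Effect | SE | One-tailed p |
|---|---|---|---|---|
| 10:10 | 0 | 8.25 | 4.681 | .047 |
| 10:10 | 5 | 8.25 | 4.530 | .043 |
| 10:10 | 10 | 8.25 | 4.044 | .028 |
| 11:9 | 0 | 8.25 | 4.704 | .048 |
| 11:9 | +5 / −5 | 7.75 / 8.75 | 4.554 | .053 / .035 |
| 12:8 | 0 | 8.25 | 4.777 | .051 |
| 12:8 | +5 / −5 | 7.25 / 9.25 | 4.629 | .067 / .031 |

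At 10:10 the largest p is at P = 0: .0475, or .048 if the stated .043 was rounded down from .0435. With SPT-B first in the larger group, the signs of P reverse.

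**How uneven could the orders be?** With 8/10, 9/10 and 8/10 matches meeting the three criteria, at least max(2, 1, 2) = 2 and at most 2 + 1 + 2 = 5 matches missed one or more. If such pairs were randomised and both members fell in the same order, each pair would move the split by one: 12:8 for two pairs, 15:5 for five.

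**Other results.** End-of-treatment effect size: 1.814/1.462 = 1.241; SD = 1.241 × √20 = 5.55; at 10:10 with P = 0 the adjusted SE is 1.274 and p moves from .080 to .086. For the two Wilcoxon results (differences 65.5 − 51 = 14.5 and 58.5 − 45.8 = 12.7), treating each p as if from a paired t-test gives at most .039 and .028 at 12:8 for period differences up to 15 points. At 15:5 with an unfavourable 15 points they reach about .17 and .18. These are rough guides, because the signed-rank test was used where normality failed.

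**The case against.** The strongest reply is that order was handled by assignment. Ten matches among 20 participants, where a match means the opposite order, is most simply read as 10:10. The four participants with modified procedures are also described as two from each order. An uneven split needs listed matches to share an order, which no passage says. Even if two pairs were randomised independently, 12:8 in either direction has probability 1/8. The count per order is cited to a table not available here, so it cannot be called missing from the plan. All of this stands.

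It is also fair that the stimuli were chosen to limit generalization across lists, that stability of the second set was checked before its treatment, that the SAP discloses the unequal timing, and that it calls the comparisons underpowered. These points make a period effect less certain but do not exclude one.

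A reader might infer that the significance of the 10-week result hinges on an undisclosed split. The documents do not support that. At the split they point to, adjustment leaves p below .05. At 12:8 with no period difference, .051 reflects the lost degree of freedom and unequal groups, not bias. The result is fragile mainly because a one-tailed p sits near .05; the two-tailed value is .086.

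The reply does not cover an order-specific effect. The intervening phase is SPT-B in one order and SPT-R in the other. If its effect on the first-treated set differs by x points between orders, the 10-week contrast at 10:10 shifts by x/2, with or without a period term. Only results by order would help to show this.

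**Conclusion.** The point holds as a cheap improvement to the analysis and its reporting. It does not show that a reported result is wrong. If the orders are 10:10 and the period effect is additive, the SPT-R minus SPT-B mean is unbiased, the paired test only loses precision when a period effect exists, and the 10-week p after adjustment is at most about .048.

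Bias arises only if the orders are unequal, which random assignment of unmatched participants does not exclude. It then equals 0.1P at 11:9 and 0.2P at 12:8, and an unfavourable 5 points gives p = .053 and .067. A favourable 5 points gives .035 and .031.

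A reader might also conclude that the two Wilcoxon results are safe whatever the split. The working supports that only up to 12:8, and only on the assumption that their p values behave like paired t results.

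**What to change.** At end of treatment, 2 weeks and 10 weeks, compare the first-minus-second-set differences between the two orders, by two-sample t or by rank-sum where normality fails. Half the difference between the order means is the SPT-R minus SPT-B effect adjusted for period. A mixed model with treatment, period and participant is an alternative. Report the effect with a 95% CI, the number of participants in each order, and the results by order. The last item is needed because a period term does not remove an order-specific effect of the intervening phase. Describe the 10-week result for first-treated sets as follow-up with intervening treatment of other words, in line with what the SAP already discloses.

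Cost: SAP wording and a re-run on data already held. One degree of freedom is spent. At 10:10 with no period difference the SE rises by 2.7% (√(19/18) = 1.027), p for 10-week percent change goes from .043 to about .047, and p for the end-of-treatment effect size goes from .080 to .086. If a sizeable period difference exists, precision improves.

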## **Percent Change Over Highest Baseline Performance**

In order to provide clinically interpretable indicators of degree of change associated with treatment, percent change scores were calculated. Separate calculations were made for each experimental set of items separated by subgrouping (SPT-R treated, SPT-R untreated, SPT-B treated, SPT-B untreated). For each participant, the highest percent accuracy score achieved in baseline was subtracted from the a) last treatment probe, b) the 2 week follow-up probe, and c) the 10 week follow-up probe. Tables 3 and 4 depict the average change scores for the group for the treated and untreated items. A negative value in Tables 3 and 4 indicates that the follow-up value was less than the highest baseline value. Note that the median scores for the group were all positive as were the 25th percentile values.

Table 3

Percent Change Over Highest Baseline: Descriptive Statistics for **Treated Items** by Treatment Condition for the Group of 20 Participants

Condition	Comparison	Mean	SD	Minimum	Maximum	Median	25 th	75 th
							%tile	%tile
Random	BL vs Tx	65.5%	20.7%	20%	100%	60%	50%	80%
	BL vs 2 wk FU	58.5%	29%	0%	100%	60%	40%	87.5%
	BL vs 10 wk FU	46.25%	32.1%	-20%	100%	50%	20%	85%
Blocked	BL vs Tx	51%	29.8%	-10%	100%	50%	30%	80%
	BL vs 2 wk FU	45.8%	29.5%	-20%	100%	40%	20%	70%
	BL vs 10 wk FU	38.0%	26.3%	-20%	80%	40%	12.5%	60%

BL = baseline; Tx = treatment; wk = week

Table 4

Percent Change Over Highest Baseline: Descriptive Statistics for Generalization (Untreated) Items by Treatment Condition for the Group of 20 Participants

Condition	Comparison	Mean	SD	Minimum	Maximum	Median	25 th	75 th
							%tile	%tile
Random	BL vs Tx	24.3%	41.7%	-67%	100%	20%	0%	60%
	BL vs 2 wk FU	23.8%	40.5%	-67%	100%	37%	0%	55%
	BL vs 10 wk FU	14.15	35.2%	-60%	100%	0%	0%	30.5%
Blocked	BL vs Tx	24.5%	41.4%	-33%	100%	20%	0%	55%
	BL vs 2 wk FU	22.7%	33.8%	-40%	100%	20%	0%	40%
	BL vs 10 wk FU	12.5%	32.7%	-60%	80%	0%	0%	34%

Comparisons of average group percent change were completed using parametric statistics (i.e., dependent t-tests, one-tailed) when possible and the nonparametric analogs when normality tests were failed (i.e., Wilcoxon Signed Rank tests). The Wilcoxon Signed Rank test indicated that the percent change in SPT-R treated items (65.5%) was statistically significantly greater than the change in SPT-B treated items (51%) for the last probe of the treatment phase: p = .022. Similarly, the sample mean percent change for SPT-R treatment items at 2-week follow-up (58.5%) was statistically significantly greater than the sample mean percent change for SPT-B treatment items at 2-weeks follow-up (45.8%): p = .016. For the 10-week follow-up comparison, a paired t-test was employed; the sample mean percent change of the SPT-R treated items (46.25%) exceeded the mean percent change of SPT-B items (38%) by an amount that is greater than would be expected by chance: p = .043. For the generalization items, no statistically significant differences were found for any of the measurement times: last treatment probe (p = .488), the 2-week follow-up probe (p = .477) and the 10-week follow-up probe (p = .396). As with the effect size data comparisons, the comparisons involving the percent change data were underpowered.

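### Twelve SPT-R versus SPT-B tests are read one by one with no stated primary test or multiplicity rule; the three positive results fail Holm over six or 12 tests

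*SAP*

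**What the plan says.** SAP, Effect Sizes: paired t-tests compare SPT-R with SPT-B, and "Normality tests were passed and one-tailed p values were obtained". For treated items the differences are reported as not significant, "associated with the end of treatment (p = .08), 2-week follow-up phases (p=.105), or 10-week follow up phases (p=.254"). For untreated items it states that "there were also no significant differences in the sample means for the three measurement conditions", and the p values listed are .186 (after treatment), .236 (2-week) and .212 (10-week).

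SAP, Percent Change Over Highest Baseline Performance: the same two conditions are compared with "parametric statistics (i.e., dependent t-tests, one-tailed) when possible and the nonparametric analogs when normality tests were failed". For treated items, the change with SPT-R at the last treatment probe "was statistically significantly greater than the change in SPT-B treated items (51%) for the last probe of the treatment phase: p = .022". The 2-week result (p = .016) is worded in the same way. At 10 weeks SPT-R is said to exceed SPT-B "by an amount that is greater than would be expected by chance: p = .043". The three generalization tests (.488, .477, .396) are reported as not significant.

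Both sections call the comparisons underpowered. Neither names a deciding measure, item type or time point, states alpha, or adjusts for the number of tests. Part of the SAP just before the Statistical Analyses heading was not available to this review, so these absences are judged on the text that can be seen.

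**The concern.** Each of the 12 p values appears to be read alone at .05. On treated items, one measure gives three significant results out of three and the other gives none, at the same time points and from overlapping probes. Without a named primary measure, the answer to whether random practice beats blocked practice depends on which table the reader turns to.

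These three results are the only positive comparative findings in the documents, and they are worded as established. The caution about power does not cover them. It concerns missed differences, whereas the risk here is of a false positive among many tests.

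**Working it through.** **Inputs.** The 12 p values are those printed in the two SAP sections. The tables are "by Treatment Condition for the Group of 20 Participants", so n = 20 pairs. Alpha is inferred as .05, because .043 is read as significant and .08 is not. One-tailed testing is explicit for the t-tests and only implied for the Wilcoxon tests, which include the p = .022 result.

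**Can the printed p values be reproduced?** Not exactly, because no within-pair correlation or individual data are given. A feasibility check uses t = d / (s_d/√20), with s_d² = s₁² + s₂² − 2ρs₁s₂. For the 10-week percent change:
- d = 46.25 − 38.0 = 8.25, and a one-tailed p of .043 on 19 df means t ≈ 1.81.
- s_d ≈ 8.25 × 4.472 / 1.81 ≈ 20.4.
- ρ ≈ (32.1² + 26.3² − 20.4²) / (2 × 32.1 × 26.3) ≈ .77, which is feasible.

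The same method gives .07, .05 and .21 for the treated effect-size tests, and .34 and .65 for the other two treated percent-change tests (only a rough check where a Wilcoxon test was used). The printed values are therefore taken as they stand.

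**Holm.** Sort the p values, multiply the k-th smallest by (m − k + 1), and never let the result fall below the one before it.

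| Family | 2-week (.016) | Last probe (.022) | 10-week (.043) |
|---|---|---|---|
| Six treated-item tests | 6 × .016 = .096 | 5 × .022 = .110 | 4 × .043 = .172 |
| All 12 tests | 12 × .016 = .192 | 11 × .022 = .242 | 10 × .043 = .430 |
| Three treated percent-change tests | 3 × .016 = .048 | 2 × .022 = .044, raised to .048 | .043, raised to .048 |

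Taking the six percent-change tests as the family gives the same values as the six treated-item tests.

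**Benjamini-Hochberg.** Multiply the k-th smallest p by m/k, then take the running minimum from the largest p down.
- Six treated tests: .066, .066, .086.
- All 12 tests: .132, .132, .172.

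**Family-wise error over 12 tests at .05.** If the tests are independent, it is 1 − .95¹² = .46. The documents give no correlations between outcomes, so dependence was simulated for one-tailed paired t-tests with n = 20. Assumed correlations ran from .5 between times, .3 between measures and .2 between item types, up to .9 throughout.
- Family-wise error falls from about 37% to about 14% across that range.
- Over 12 tests, the smallest p (.016) adjusts to about .15 at the low end and .05 at the high end (.054 in one run, .058 in another). Under independence it is about .18.
- Over the six treated tests it adjusts to about .08 at the low end and .04 at the high end (.09 under independence).

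**Direction of the two measures.** All six treated-item means favour SPT-R. Table 1 shows 9.203 against 7.389, 8.643 against 6.861, and 6.84 against 6.144. Table 3 shows 65.5% against 51%, 58.5% against 45.8%, and 46.25% against 38.0%.

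**The case against.** The strongest reply is that 12 is too large a family. The Protocol, under Probes, separates acquisition on treated items from response generalization on untreated ones, and these are different constructs. That point stands, which is why the six treated-item tests are the better main family. The Holm result there is still negative.

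A second reply is that Holm is conservative for correlated tests. This also stands in part: over six tests the smallest p is borderline once correlation is allowed for (about .04 to .08), so one result might survive a joint test. It cannot be claimed that no adjustment could rescue any of the three.

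A third is that percent change was introduced to be clinically interpretable, so its three treated-item tests form their own family. All three then pass Holm at .048. But the visible text does not declare that family or make percent change primary. The margin is also thin: if the p values were doubled to two-sided, Holm would give 3 × .032 = .096.

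A reader might infer selective reporting. The documents do not support that, since all 12 p values and both sets of descriptive tables are printed. A reader might also infer that the two measures contradict each other. They do not: they agree in direction and differ in construction. At the end of treatment, effect size uses five baseline probes and the final two treatment probes, scaled by the baseline SD, while percent change uses the highest baseline score and the last probe only.

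**Conclusion.** The point holds as a matter of interpretation. None of the three positive results survives Holm or Benjamini-Hochberg over the six treated-item tests or over all 12; they pass Holm only in a family of three that the visible text does not declare. The SPT-R advantage on treated items is therefore nominal: it reaches unadjusted significance on one of two measures.

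It would go too far to conclude that the treatments do not differ. All treated-item means favour SPT-R, and with 12 independent null tests the chance of three or more at or below .05 is only .020 (higher with positive correlation). The evidence is suggestive but not confirmatory.

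The conclusion rests on an inferred alpha of .05, on the printed p values being correct, and on no primary test having been specified in the part of the SAP not available here. The Holm figures need no assumption about correlation; the simulated ranges depend wholly on the assumed correlations.

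**What to change.** In both SAP sections, print Holm-adjusted p values over the six treated-item tests beside the unadjusted ones. Treat the six generalization tests as a separate family, and show the 12-test adjustment as a sensitivity analysis. A joint sign-flip max-t test, swapping each participant's SPT-R and SPT-B labels across all outcomes together, may be added and reported whatever it shows. Any family chosen now is post hoc, and the text should say so.

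Replace the claims of significance and of exceeding chance for the three treated percent-change results. The text should say that the SPT-R advantage is nominal and exploratory, reaches unadjusted significance on one of two measures, and is not significant under Holm.

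State alpha, the sidedness of the Wilcoxon tests and the direction tested. The direction matters because the generalization result at the last treatment probe has SPT-R slightly below SPT-B (24.3% against 24.5%) with p = .488, whereas a one-tailed paired t-test for SPT-R above SPT-B would give a p above .5.

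If a primary test was specified elsewhere, cite it and base the conclusion on it.

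The cost is one analysis step on existing data and some rewording. The headline comparison becomes less favourable.
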